**3.10.5. Concomitant Medication Dates**

While concomitant medication dates will not be directly imputed, partial concomitant start and stop dates will be considered for purposes of identifying prior and/or concomitant status. In general, partial dates with any ambiguity towards prior/concomitant status will be considered concomitant; only partial dates that can clearly indicate prior status will be considered as such.

**3.11. Visit Windows**

Every effort should be made to ensure that all visits occur according to the protocol SOA, including any dropouts.

**3.11.1. Therapeutic Dose Start Date and Primary Timepoint**

Efficacy data will be summarized formally at the primary timepoint, after 52 weeks on therapeutic dose.

Setmelanotide or placebo equivalent will be administered at starting doses in all patients and subsequently up-titrated towards the target therapeutic dose, CCI dependent. CCI

[REDACTED]

[REDACTED]

[REDACTED]

[REDACTED]

CCI  
.

To identify the primary timepoint, the following steps will be utilized:

- Calculate the number of days from therapeutic dose start date for all on-site visits excluding bridging visits
- The non-missing, on-site visit occurring closest to day 365 within a window of 305 to 425 days from therapeutic dose start date will be selected
- If multiple results are equidistant from Day 365 (from the therapeutic dose start date), the latest of these equidistant results is selected
- If no results have been reported within days 305 to 425 from therapeutic dose start date, then the primary timepoint is considered missing

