### Treatment Period

To enter the Treatment Period on Day 1 and prior to randomization, the trial center must confirm that patients have completed the Screening assessments, including the e-diary at least 4 of the 7 days prior to the baseline visit. If the e-diary is not appropriately completed before the baseline visit, patients may be asked to complete the e-diary collection and re-schedule randomization and the baseline visit if the remaining visit window allows. Throughout the trial, patients (or caregivers) will need to complete the e-diary entries.

The Treatment Period is intended to last until each patient has been dosed for 52 weeks on a therapeutic regimen (56 weeks to 60 weeks). Trial drug administration details are provided in [Section 5.5.3](#) and

**Table 6.** During the Treatment Period, patients will attend in-clinic visits and may attend at home tele-health visits at Weeks 8, 16, 20, 28, 36, 44, 52 at the discretion of the investigator. Patients and caregivers will complete the assessments listed in the SoA (Table 1). Detailed assessment information is provided in Section 6.

CCI

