## 1.2. Schedule of Assessments

**Table 1: Schedule of Assessments**

Trial Period/ Procedure*	Screening	Treatment Period															EOT †† (after 52 weeks on a therapeutic regimen)		ETT	SFV 	Bridging Visits**
		V1 	Call	V2	V3 †	V4	V5 †	V6 †	V7	V8 †	V9	V10 †	V11	V12 †	V13	V14 †	V15 ††	V16 ††			
Clinic Visit Number																					Every 12 weeks
Trial Day	-56 to -1	1	8	22	50	78	106	134	162	190	218	246	274	302	330	358	386	414			
Trial Week	-8 to -1	1	2	4	8	12	16	20	24	28	32	36	40	44	48	52	56	60			
Visit Window (days)	-	-	±4	±4	±4	±4	±4	±4	±4	±4	±4	±4	±4	±4	±4	±4	±4	-4 weeks +4 days		±4	±2 weeks
Informed consent/assent 	X																				
Inclusion/ exclusion criteria review	X	X																			X
Medical history	X	X																			
Diagnostic history 	X	X																			
Randomization		X																			
Physical examination 	X	X				X							X				X ††	X	X	X	X
Comprehensive skin examination 	X			X													X ††	X	X		X
Fitzpatrick scale		X																			

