#### 5.1.3. End of Treatment

The End of Treatment (EOT) visit will occur as an in-person clinic visit after 52 weeks on a therapeutic regimen, which is the final planned week of dosing with trial treatment. At the EOT, patients who complete 52 weeks on a therapeutic regimen and complete assessments through the EOT visit may be eligible to enter an open-label LTE trial or attend Bridging visits with open-label setmelanotide if the LTE is not yet available. Patients must meet the LTE eligibility criteria and should discuss eligibility with the Investigator.

CCI

All patients who discontinue treatment prematurely should attend an ETT Visit as soon as possible after the last dose of trial treatment. Patients who discontinue treatment but remain enrolled in the trial should continue to complete assessments (as Retained Dropouts). These patients will be required to complete the SFV as applicable following the ETT (Section 5.1.4). Patients who discontinue treatment prematurely are not eligible to enroll in the optional LTE trial. Exceptions may be made in consultation with the Sponsor.

Patients who discontinue prematurely and withdraw from the trial will not be required to complete the SFV following the ETT.

If the ETT Visit occurs 4 weeks or later following the last dose of trial treatment, then the ETT Visit will replace the SFV if no AEs are being monitored.

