#### 5.1.4. Safety Follow-up Visit

An SFV will occur as an in-person visit 14 days ( $\pm 4$  days) after the last dose of trial treatment. The SFV is not required for patients who complete the treatment period and either:

- enroll in the LTE (or bridging visits if the LTE is not yet available) or transition to another qualified Rhythm study (e.g., managed access)
- transition to a commercially available Rhythm MC4R agonist regimen

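### The primary-timepoint rule in SAP 3.11.1 leaves out only bridging visits and gives End of Treatment no priority, so it can select an off-drug Safety Follow-up weight for some treatment completers

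*SAP*

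**What the plan says.** SAP 3.11.1 builds the primary timepoint in three steps. The candidate set is defined by "Calculate the number of days from therapeutic dose start date for all on-site visits excluding bridging visits". The record chosen is "The non-missing, on-site visit occurring closest to day 365 within a window of 305 to 425 days" from the therapeutic dose start. If two records are equally distant from day 365, "the latest of these equidistant results is selected". Being on treatment is not a condition, the SFV is not mentioned, and the EOT visit has no precedence.

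Protocol 5.1.4 states that "An SFV will occur as an in-person visit 14 days", with a tolerance of 4 days either way, after the last dose. Protocol Table 1 schedules height and weight at that visit. The SFV is waived for completers who enter the long-term extension (LTE) or bridging visits, or who transition to another qualified sponsor study or a commercial regimen.

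Under Protocol 5.1.3, the EOT "visit will occur as an in-person clinic visit after 52 weeks on a therapeutic regimen". Table 1 places it at V15 (Day 386, ± 4 days) or V16 (Day 414, from 4 weeks early to 4 days late).

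SAP 3.11.2 treats the intermediate visits differently. For Visits 2, 4, 7, 9 and 11 the value recorded for that visit is used whatever its timing, and windowing applies only if that value is missing.

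**The concern.** The endpoint is percent change in BMI after about 52 weeks on a therapeutic regimen. For a patient who finishes treatment, the EOT weight is the measurement intended to capture it. The rule can set that value aside for a weight taken 10 to 18 days after dosing stopped, because it looks only at distance from day 365. The safeguard that SAP 3.11.2 gives to the intermediate visits is missing for the visit that carries the primary analysis.

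Three things depend on the choice:

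- The weight selected feeds the primary endpoint and, through SAP 4.3.5, both BMI responder key secondary endpoints. A patient close to the 5% threshold could change status.
- The treatment-policy strategy does not cover the substitution. SAP 4.3.1 applies that strategy to early discontinuation, wrong treatment, interruption and non-adherence. Planned completion is none of these.
- SAP 3.10.2 separates patients who are off treatment at the primary timepoint from on-treatment completers before imputation. A completer represented by an SFV weight is off drug on that date, and the SAP does not say which group applies. If it is the first, someone who completed the planned course would inform the retrieved-dropout model.

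**Working it through.** **Inputs.** The selection rule, window and tie rule are from SAP 3.11.1. EOT days and windows are from Protocol Table 1, and SFV timing from Protocol 5.1.4. The therapeutic start day *s* is unknown because its definition in SAP 3.11.1 is redacted. I assume that the last dose is on the EOT day, so the EOT-to-SFV gap *g* is 10 to 18 days.

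**1. Reproduce the plan's 52 weeks.** 52 × 7 = 364 days. Table 1 labels Day 22 as Week 4 and Day 50 as Week 8. A therapeutic start at those visits gives 386 − 22 = 364 and 414 − 50 = 364, so the schedule and the EOT definition agree exactly.

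**2. Switch point.** Let EOT fall on therapeutic day *e*, before day 365. The SFV falls on *e* + *g*. It is selected when |*e* + *g* − 365| ≤ |*e* − 365|, with equality counting because the later record wins a tie. This reduces to *e* ≤ 365 − *g*/2:

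- *g* = 10: *e* ≤ 360
- *g* = 14: *e* ≤ 358
- *g* = 18: *e* ≤ 356

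**3. Start day on the nominal schedule, *g* = 14.** 386 − *s* ≤ 358 gives *s* ≥ 28. 414 − *s* ≤ 358 gives *s* ≥ 56. Each threshold is one day later if the start date counts as day 1.

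| Therapeutic start | EOT study day | EOT therapeutic day (distance from 365) | SFV therapeutic day (distance) | Selected |
|---|---|---|---|---|
| Day 22 | 386 | 364 (1) | 378 (13) | EOT |
| Day 28 | 386 | 358 (7) | 372 (7) | SFV, on the tie |
| Day 29 | 386 | 357 (8) | 371 (6) | SFV |
| Day 50 | 414 | 364 (1) | 378 (13) | EOT |
| Day 56 | 414 | 358 (7) | 372 (7) | SFV, on the tie |
| Day 57 | 414 | 357 (8) | 371 (6) | SFV |

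Days 29 and 57 correspond to 4 and 8 full weeks before therapeutic dosing (1 + 28 and 1 + 56). That is one reading of the synopsis, which puts total dosing at 56 to 60 weeks: 56 − 52 = 4 and 60 − 52 = 8.

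**4. Early V16.** The V16 window runs from Day 414 − 28 = 386 to Day 418. With a start on Day 50, a V16 on Days 386 to 408 falls on therapeutic days 336 to 358, and a 14-day SFV is selected. For example, V16 on Day 400 is day 350 (distance 15) and its SFV is day 364 (distance 1).

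**5. EOT on time.** With EOT within 4 days of day 364 (days 360 to 368) and *g* from 10 to 18, the SFV is selected at one corner only: EOT at 360 with *g* = 10, where both distances are 5. If the start date counts as day 1, that tie also disappears.

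**6. Effect on the mean, as illustration only.** The shift in the setmelanotide mean is the share of patients whose value switches times the off-drug regain. The documents give neither figure. Assuming 5% to 20% and 1 to 2 BMI percentage points, the range is 0.05 × 1 = 0.05 to 0.20 × 2 = 0.4 points, against a planned difference of 10 points.

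**The case against.** A reader might infer that completers seen on the scheduled days will generally have the SFV weight selected. The documents do not support that. The result needs a therapeutic start on about Day 28 or later with EOT on Day 386, or about Day 56 or later with EOT on Day 414, and the definition that would settle this is redacted. Counting titration in full elapsed weeks while taking EOT from the schedule's week labels mixes two conventions and puts EOT at day 357, which is 51 weeks and short of the EOT definition. On one consistent convention EOT is at day 364 and the rule works. The wide V16 window may exist so that EOT can follow each patient's own therapeutic start. This part of the objection stands, so the point has to be conditional.

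It is also correct that many completers may need no SFV, that the documents contain no data on regain in the two weeks after stopping, and that any such regain in the setmelanotide arm would shrink the apparent effect rather than create a false success.

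The objection does not remove the gap in the rule. Protocol 5.5.3.2 allows a planned escalation to be delayed while treatment is limited to about 60 weeks, and Table 1 accepts a V16 up to 4 weeks early. Either can bring EOT to day 358 or earlier without any assumption about the standard titration length, although such an EOT would fall short of 52 therapeutic weeks as defined.

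**Conclusion.** The concern holds in conditional form. As written, SAP 3.11.1 permits an off-drug SFV weight to replace an observed EOT weight for treatment completers who attend an SFV. With a 14-day gap it does so whenever EOT is on therapeutic day 358 or earlier. It does not do so when EOT falls at day 364 as defined.

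Confidence is high that the rule permits this and low to moderate on how often it would occur. The effect on the mean is probably small, and nothing here threatens the planned power of about 99.5%. The reason to act is that the derivation of the primary endpoint should not depend on which visit happens to lie nearer to day 365.

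The point is limited to measures collected at the SFV. It might be thought to reach hunger, the third key secondary endpoint, but Table 1 schedules neither the hunger questions nor waist circumference at that visit.

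**What to change.** In SAP 3.11.1, add that for patients who complete treatment the EOT value is the primary-timepoint value when it lies within days 305 to 425 of the therapeutic dose start, that the SFV is not a candidate visit, and that the nearest-to-365 rule applies only when the EOT value is missing. This extends to the primary timepoint the convention that SAP 3.11.2 already uses for the intermediate visits. Leave the rule unchanged for patients who stop early, whose off-treatment weights belong in a treatment-policy analysis.

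Apply the change to weight, BMI and their derivatives, including both BMI responder key secondary endpoints, and to other measures taken at the SFV such as vital signs and safety laboratory tests. Hunger and waist circumference need no change.

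The schedule days in Table 1, the 52-week EOT definition and the 56-to-60-week duration in the synopsis should also be reconciled, so that the expected therapeutic day of EOT is clear.

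The cost is one sentence in the SAP and one filter in the derivation program, made before unblinding. With the SFV removed, EOT is selected on the nominal days under both readings of the start date: day 364 (start Day 22 or 50) and day 357 (start Day 29 or 57).

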3.11.2. Efficacy Windowing for Patients

As noted in Section 3.10.2, RD MI and washout MI methodologies will impute based on results from baseline, Visit 2, Visit 4, Visit 7, Visit 9, Visit 11, and the primary timepoint. To ensure that captured data is used to the greatest extent possible, expanded windows as compared to the SOA will be considered. Note that visit windowing and use of on-site additional, unscheduled, or early termination visits will only occur if the specific visit as recorded and tabulated per the CRF is missing. That is, for on-site Visits 2, 4, 7, 9, and 11, the value collected directly from the CRF will be used, regardless of timing of that visit. If there is no collected value for a given visit per the CRF, the missing value will be replaced from other, non-missing, on-site visits (excluding bridging visits) based on the target analysis windows outlined in Table 3-1. Similar to primary timepoint handling, if there are multiple records equidistant from the target day, the latest of the equidistant records will be utilized.

Table 3-1 Efficacy Windowing for MI Models

Visit	Visit 2	Visit 4	Visit 7	Visit 9	Visit 11
SoA Target Visit Day	22	78	162	218	274
Target Analysis Visit Window	14, 50	51, 120	121, 190	191, 246	247, 304

3.12. Interim Analyses, Timing of Planned Analyses, and Cohorts

No formal interim analysis is currently planned before the completion of the pivotal cohort for this study. However, various data cuts may occur after completion of the pivotal cohort in support of regulatory submissions. The timing of these data cuts and the number of patients included in each analysis will take into account specific requests from regulatory agencies and applicable regulatory guidance. The rationale of each analysis will be documented.

3.12.1. Timing of Planned Analyses and Cohorts

While this study is powered assuming 120 patients, there are additional Japanese Pharmaceuticals and Medical Devices Agency (PMDA) guidance under consideration. Namely,

12 Japanese patients are to be enrolled and dosed for regulatory considerations. It is expected that these 12 patients will not be enrolled within the first 120 dosed patients and that there may be slight over-enrollment in total patient count to achieve the 12 Japanese patients.

As such, there are two currently planned analyses for the RM-493-040 study.

The pivotal analysis is planned for when 120 patients have completed or discontinued from the study, in accordance. This analysis will focus on the pivotal cohort, defined as the first 120 subjects dosed in any region who have completed the trial and any patients who discontinued after receiving their first dose of study drug.

Any patients beyond this pivotal set of 120 patients at the time of the pivotal analysis will have their data combined with the data of the pivotal set of patients and be analyzed together as ‘all patients’ at the time of the pivotal analysis. Summaries of all patients at the time of the pivotal analysis will be considered as additional, supportive information.

Formal hypothesis testing and success/failure conclusion of the study will be based off the pivotal cohort.

An additional analysis is planned for when the 12 Japanese patients have completed or discontinued from the study. Analyses on all patients will be rerun at this time. To support access and regulatory considerations for the PMDA, specific primary, key secondary, and safety analyses may be run on just the Japanese patients with supportive consistency and exploratory evaluations. Any such analyses will be outlined in this SAP but will be subject to the additional analysis only and should not be considered as a core component of the regulatory package except for any PMDA submission.

4. STUDY ANALYSES

4.1. Disposition

Patient disposition will be tabulated by randomized group and include the number screened, the number randomized, the number treated in total, the number dosed with setmelanotide, the number dosed with placebo, the number in each patient population for analysis, and the number who withdrew prior to completing the treatment and reason(s) for withdrawal. Patient disposition will be summarized for the pivotal cohort of patients and all patients. A separate patient disposition will be provided for Japanese patients only.

A by-patient data listing of study completion information including the reason for premature treatment withdrawal will be presented for all patients.

4.2. Demographics and Baseline Characteristics

Demographics and baseline characteristics information will be summarized by treatment group and overall. Age, height, weight, waist circumference, BMI, BMI P95, and BMI Z-Score at baseline will be summarized using descriptive statistics, as applicable. The number and percentage of participants in each age group (<12 years old, ≥12 to <18 years old, ≥18 years old), sex, ethnicity, race, and subpopulation (Japanese vs non-Japanese) will also be presented. Skin type as measured by the Fitzpatrick Classification Scale as defined in Table 4-1, will also be summarized. Patient demographics and baseline characteristics will be summarized for the mITT for pivotal patients and all patients. A separate summary of patient demographics and baseline characteristics will be provided for Japanese patients only.

Table 4-1 Fitzpatrick Classification Scale

Skin Type	Skin Color	Characteristics
I	White; very fair; red or blond hair; blue eyes; freckles	Always burns, never tans
II	White; fair; red or blond hair; blue, hazel, or green eyes	Usually burns, tans with difficulty
III	Cream white; fair with any eye or hair color; very common	Sometimes mild burn, gradually tans
IV	Brown; typical Mediterranean Caucasian skin	Rarely burns, tans with ease
V	Dark Brown; mid-eastern skin types	Very rarely burns, tans very easily
VI	Black	Never burns, tans very easily

Source: [Fitzpatrick 1975](#)

Patient demographic and baseline characteristics data will be provided in by-patient listings.

4.2.1. Medical and Diagnostic History

Medical history will be summarized in a table by MedDRA System Organ Class (SOC) and Preferred Term (PT) frequencies by treatment group and overall for the SA. Summaries will include pivotal and all patients.

A by-patient listing of medical history will be provided.

### 4.3. Efficacy Evaluation

In general, efficacy analyses will be conducted using the mITT population. Unless stated otherwise, the analysis on hunger score data will be provided for patients  $\geq 12$  years of age and  $< 12$  years of age. Descriptive summaries will be provided for both age groups for their corresponding questionnaire tools (due to the different hunger score questionnaire tools).

#### 4.3.1. Primary Estimand

The population of the primary estimand is among participants (aged 4 years or older) with documented evidence of acquired HO and weight gain according to the inclusion/exclusion criteria. Participants will receive either active setmelanotide or placebo, where dose-escalation will occur based upon an **CCI** [REDACTED]. The primary analysis will be executed using the mITT analysis set, including all randomized patients receiving at least one dose of study drug, grouped as randomized.

The variable is mean percent change from baseline in BMI after 52 weeks of treatment with either setmelanotide or placebo.

Intercurrent events: Patients who discontinue treatment prior to study discontinuation will be handled via the treatment policy strategy, in which all collected measurements will be included in the statistical analyses. Other potential intercurrent events such as receiving the wrong treatment, treatment interruption, and non-adherence to study drug will also be handled via the treatment policy strategy whereby all collected measurements will be included in the statistical analyses.

Any on-study death will be handled via the composite strategy, in which death is considered a sufficiently unfavorable outcome and the patient will have their corresponding change and percent change from baseline artificially set to 0.

The population level summary is the difference between treatment groups (setmelanotide and placebo) in mean percent change from baseline in BMI at Week 52, obtained from an analysis of covariance (ANCOVA) model, with unequal variance to account for possible unequal residual variances, based on the outcomes of 100 imputed datasets combined using Rubin's Rule (Little and Rubin 2002). Multiple imputation assuming missing not at random (MNAR) will be used as the primary approach for missing data and will model the missing measurements based on known measurements from retrieved dropouts in the same treatment group. If insufficient retrieved dropouts exist to provide a reliable multiple imputation model, wash-out imputation will be used where missing values for subjects on active drug will be imputed with observed baseline and data from the placebo group. No intermediate values from the active treatment group would be used in this approach. Further technical details are found in [Section 3.10.2](#).

The robustness of the primary estimand will be assessed through sensitivity analysis using two-dimensional tipping point.

### 4.3.2. Primary Efficacy Analysis

The primary efficacy endpoint of this study is the mean percent change from baseline in BMI after 52 weeks of treatment with the therapeutic regimen of either setmelanotide or placebo.

The statistical hypothesis for the primary efficacy endpoint is:

$$H_0: \mu_t - \mu_p \geq 0 \text{ vs } H_1: \mu_t - \mu_p < 0$$

where  $\mu_t$  is the mean percent change in BMI from baseline after approximately 52 weeks on a therapeutic regimen in setmelanotide group, and  $\mu_p$  is the mean percent change in BMI from baseline after approximately 52 weeks in placebo group.

The primary endpoint will be conducted on the mITT utilizing BMI values resultant from the multiple imputation process as outlined in [Section 3.10.2](#). The difference between setmelanotide and placebo after 52 weeks on therapeutic dose will be estimated using an ANCOVA model with unequal variance to account for possible unequal residual variances. The model will be adjusted with stratification factors of age group ( $\geq 18$  years old,  $\geq 12$  and  $< 18$  years old, and  $< 12$  years old) and subpopulation (Japanese and non-Japanese) as appropriate. This difference will be estimated for each of the 100 imputed datasets. The outcomes from the 100 imputed datasets will be combined using Rubin's Rule ([Little and Rubin, 2002](#)) through SAS PROC MIANALYZE to provide an overall estimate of least squares (LS) mean difference with corresponding 95% confidence intervals (CI) and p-value. The success criterion for the primary hypothesis requires the rejection of the null hypothesis at the 2-sided 0.05 significance level.

While formal hypothesis testing will be considered based on pivotal patients, the primary analysis will also be conducted for all patients.

The primary analysis will be repeated for Japanese patients to explore consistency of effect for the PMDA. Consistency will be determined as an observed treatment effect in Japanese patients of at least 50% of the observed, overall treatment effect (seen in all patients), in alignment with PMDA Method 1. All patients are the basis for comparison as this is the set of patients that consists of all 12 Japanese patients.

The actual, change from baseline, and percent change from baseline for observed values of BMI will be summarized descriptively by visit for pivotal and all patients in the mITT, as needed. Additional descriptive summaries will be provided by age category for pivotal and all patients as well as for Japanese/non-Japanese subgroup for all patients, as needed.

Percent change from baseline in BMI in observed values will be presented graphically by treatment group and visit, with standard error bars included, for the mITT for pivotal and all patients. The x-axis will include visit in weeks and the y-axis will represent the observed mean  $\pm$  SE of percent change from baseline.

A by-patient listing for BMI observed values will be provided.

